Appendix F Adverse events of special interest

Adverse events of special interest (AESI) for this protocol include but are not limited to potential immune-mediated diseases; representative examples of AESI are listed below. Updates to AESI will be provided as an appendix to the HVTN 304 Study-specific Procedures (SSP).

Neuroinflammatory disorders	Musculoskeletal disorders	Skin disorders

 • Cranial nerve disorders, including paralyses/paresis (eg, Bell's palsy) • Optic neuritis • Multiple sclerosis • Transverse myelitis • Guillain-Barré syndrome, including Miller Fisher syndrome and other variants • Acute disseminated encephalomyelitis, including site specific variants: eg, non-infectious encephalitis, encephalomyelitis, myelitis, myeloradiculoneuritis • Myasthenia gravis, including Lambert-Eaton myasthenic syndrome • Immune-mediated peripheral neuropathies and plexopathies, (including chronic inflammatory demyelinating polyneuropathy, multifocal motor neuropathy and polyneuropathies associated with monoclonal gammopathy). • Narcolepsy 	
 • Systemic lupus erythematosus and associated conditions • Systemic scleroderma (Systemic sclerosis), including diffuse systemic form and CREST syndrome • Idiopathic inflammatory myopathies, including dermatomyositis • Polymyositis • Antisynthetase syndrome • Rheumatoid arthritis, and associated conditions including juvenile chronic arthritis and Still's disease • Polymyalgia rheumatica • Spondyloarthritis, including ankylosing spondylitis, reactive arthritis (Reiter's Syndrome) and undifferentiated spondyloarthritis • Psoriatic arthropathy • Relapsing polychondritis • Mixed connective tissue disorder 	
 • Psoriasis • Vitiligo • Erythema nodosum • Autoimmune bullous skin diseases (including pemphigus, pemphigoid and dermatitis herpetiformis) • Alopecia areata • Lichen planus • Sweet's syndrome • Localized Scleroderma (Morphea) • Cutaneous lupus erythematosus
Metabolic disorders		

 • Addison's disease • Autoimmune thyroiditis (including Hashimoto thyroiditis) • Diabetes mellitus type I • Grave's or Basedow's disease 		
Vasculitides	Blood disorders	Others

 • Large vessels vasculitis including: giant cell arteritis such as Takayasu's arteritis and temporal arteritis. • Medium sized and/or small vessels vasculitis including: polyarteritis nodosa, Kawasaki's disease, microscopic polyangiitis, Wegener's granulomatosis, Churg-Strauss syndrome (allergic granulomatous angiitis), Buerger's disease (thromboangiitis obliterans), necrotizing vasculitis and anti-neutrophil cytoplasmic antibody (ANCA) positive vasculitis (type unspecified), Henoch-Schonlein purpura, Behcet's syndrome, leukocytoclastic vasculitis. 	
 • Autoimmune hemolytic anemia • Autoimmune thrombocytopenia • Antiphospholipid syndrome • Pernicious anemia • Autoimmune aplastic anemia • Autoimmune neutropenia • Autoimmune pancytopenia 	
 • Autoimmune glomerulonephritis (including IgA nephropathy, glomerulonephritis rapidly progressive, membranous glomerulonephritis, membranoproliferative glomerulonephritis, and mesangiproliferative glomerulonephritis) • Ocular autoimmune diseases (including autoimmune uveitis and autoimmune retinopathy) • Autoimmune myocarditis cardiomyopathy • Sarcoidosis • Stevens-Johnson syndrome • Sjögren's syndrome • Idiopathic pulmonary fibrosis • Goodpasture syndrome • Raynaud's phenomenon
Gastrointestinal disorders		

 • Celiac disease • Crohn's disease • Ulcerative colitis • Ulcerative proctitis 		
Liver disorders		

 • Autoimmune cholangitis • Autoimmune hepatitis • Primary biliary cirrhosis • Primary sclerosing cholangitis 		

Appendix H Version history

The Protocol Team may modify the original version of the protocol. Modifications are made to HVTN protocols via clarification memos, letters of amendment, or full protocol amendments.

The version history of, and modifications to, Protocol HVTN 304 are described below.

Protocol history and modifications

Date: January 11, 2023

Protocol version: Version 2.0

Protocol modification: Full protocol amendment 1

- Item 1 Revised in Section 5.1.1, *Inclusion criteria*, inclusion criterion #13 :blood pressure range
- Item 2 Deleted in Section 9.1, *Adverse events*: creatinine as an exception to the DAIDS Table for Grading the Severity of Adult and Pediatric Adverse Events
- Item 3 Revised in Section 9.6, *Safety pause and prompt PSRT AE review*, Table 9-1: pause rules for related SAEs
- Item 4 Revised in Appendix C, *Sample informed consent form*, item 23: study-related injury language and role of Inovio Pharmaceuticals, Inc. and Access to Advanced Health Institute (AAHI)
- Item 5 Revised in Appendix B, *Visit windows*: lower allowable window for AESI contact
- Item 6 Minor formatting changes throughout
- Item 7 Added to Appendix H, *Version history*: contents of this amendment

Date: November 3, 2022

Protocol version: 1.0

Original protocol

---

## SAP Modification History

The version history of, and modifications to, this statistical analysis plan are described below.

SAP Version	Modification
1.0	Initial
2.0	Added BCP assay (section 8.3)
3.0	Added ADCC, ICABA, BAMA, and EMPEM assays (sections 8.4-8.7)
4.0	Added differential binding tables and figures to BAMA (section 8.6) Updated BCP markers and removed comparison tables (section 8.3)

## 1 OVERVIEW

The following describes the Statistical Analysis Plan (SAP) for the analysis of immunogenicity data from HVTN 304 for Protocol Team (PT) reports of immunogenicity data, and for the Final Study Report (FSR) of Immunogenicity.

## 2 PROTOCOL SUMMARY

### Title

A phase 1 open-label clinical trial to evaluate the safety and immunogenicity of synthetic DNAs encoding a native-like HIV Env Trimer and Interleukin-12 (INO-6160), alone or in a prime-boost regimen with 3M-052-AF + Alum adjuvanted VRC HIV Env Trimer 4571 in adult participants without HIV.

### Design

This is a randomized open-label trial to examine the safety and immunogenicity of INO-6160 (synthetic DNAs encoding a native-like HIV Env Trimer and Interleukin-12), alone or in a prime-boost regimen with VRC HIV Env Trimer 4571 adjuvanted with 3M-052-AF + Alum. The primary hypothesis is that the vaccine regimen will elicit HIV-1 envelope protein-specific binding antibody (Ab) and T-cell responses.

### Study products, diluents, and electroporation device

- INO-6160: sD-NLT-AB05 co-formulated with IL-12 DNA (pGX6001): sD-NLT-AB05 consists of a single plasmid, pGX1060 (in pGX0001 vector backbone), encoding a soluble stabilized native-like trimer derived from clade A isolate BG505. pGX6001 (pGX0003 vector backbone), contains a dual promoter system for expression of both the human IL-12 p35 and p40 genes necessary for production of the active heterodimeric IL-12 protein. The plasmid ratio for the coformulated drug product is 4:1 (0.8 mg pGX1060/0.2 mg pGX6001) per 0.1 mL/1 mg injection. The coformulation, INO-6160, in water-for-injection (WFI), is supplied at a concentration of 10 mg/mL and a volume of 0.4 mL in 2-mL glass vials.
- Trimer 4571: HIV-1 Env Trimer 4571 (VRC-HIVRG096-00-VP) is a soluble protein that consists of BG505 DS-SOSIP.664 gp140 Env and is supplied as a sterile, aqueous, buffered solution filled into single-dose vials at a concentration of 500 mcg/mL and a volume of 1.2 mL in 3-mL glass vials. Trimer 4571 is provided by the Dale and Betty Bumpers Vaccine Research Center (VRC) and will be used at a dose of 100 mcg.
- 3M-052-AF adjuvant: This adjuvant is an aqueous formulation (AF) of the small molecule imidazoquinoline, which acts as a toll-like receptor (TLR) 7/8 agonist. 3M-052-AF is supplied at a concentration of 50 mcg/mL and a fill volume of 0.4 mL in 2-mL glass vials.
- Aluminum Hydroxide Suspension, Adjuvant: Aluminum hydroxide suspension (Alum) is composed of Alhydrogel 2% (Brenntag Biosector, Frederikssund, Denmark) diluted with WFI to a concentration of 5 mg/mL. It is supplied as a sterile, pyrogen-free suspension filled into single-dose vials at a volume of 0.7 mL.
- Electroporation device: The Inovio CELLECTRA Adaptive Constant Current Electroporation (EP) Device is a portable, battery-powered medical device designed to facilitate the introduction

of DNA into skin through EP. The Inovio CELLECTRA 2000 will be used for intradermal (ID) delivery following Mantoux injection of the DNA vaccine and is provided by Inovio Pharmaceuticals.

### Study participants

20 healthy volunteers without HIV, 18 through 55 years of age in the United States.

### Study plan and schema table

Participants will be evaluated for safety and immune responses through blood collection at specified timepoints throughout the study. The study schema is below:

Group	N	Product/Dose	Route	Injection Schedule			
				Month 0	Month 1	Month 3	Month 6
1	10	INO-6160 / 2.0 mg	ID EP	X	X	X	X
2	10	INO-6160 / 2.0 mg	ID EP	X	X	X	X
		Trimer-4571 / 100 mcg 3M-052-AF (5 mcg) + Alum (500 mcg)	IM	--	--	X	X
Total	20*						

Enrollment was restricted to 1 participant per day for the first 5 participants (across both arms) and enrollment paused after the first 5 participants were enrolled. The Protocol Safety Review Team (PSRT) reviewed cumulative safety information for all participants recorded through the visit scheduled 2 weeks post first vaccination for the first 5 participants and determined it was safe to proceed with full enrollment. The full enrollment was completed as of July 7, 2023 with a total of 20 participants.

### Duration per participant

12 months of scheduled clinic visits (main study) and an AESI health contact at month 18.

### Estimated total study duration

24 months (includes enrollment, planned safety holds, follow-up, and AESI health contact).

### Study sites

The HIV Vaccine Trials Network (HVTN) Clinical Research Sites (CRSs) will be located in the US and will be further specified in the Site Announcement Memo.

## 3 OBJECTIVES AND ENDPOINTS

### 3.1 Primary objectives and endpoints

Objectives	Endpoints
------------	-----------

1. To evaluate the safety and tolerability of 2 doses of sD-NLT-AB05 + IL-12 DNA adjuvant followed by 2 doses of sD-NLT-AB05 + IL-12 DNA adjuvant alone or in combination with Trimer 4571 adjuvanted with 3M-052-AF + Alum
  - a) Local and systemic reactogenicity signs and symptoms will be collected for a minimum of 2 weeks following receipt of any study vaccine
  - b) Serious adverse events (SAEs), medically attended adverse events (MAAEs), adverse events of special interest (AESIs) and AEs leading to early participant withdrawal or permanent discontinuation will be collected throughout the study and for 12 months following any receipt of study product. Additionally, all adverse events will be collected for 30 days after any receipt of study vaccination.
2. To evaluate the immunogenicity of 2 doses of sD-NLT-AB05 + IL-12 DNA adjuvant followed by 2 doses of sD-NLT-AB05 + IL-12 DNA adjuvant alone or in combination with Trimer 4571 adjuvanted with 3M-052-AF + Alum
  - a) Response rate and magnitude of vaccine-matched IgG binding Ab responses as assessed by multiplex assay 2 weeks following the fourth vaccination
  - b) Response rate and magnitude of CD4+ and CD8+ T-cell responses measured by flow cytometry, to HIV-1-specific Env peptide pools, 2 weeks following the fourth vaccination

### 3.2 Secondary objectives and endpoints

#### Objectives

1. To further evaluate and compare the ability of 2 doses of sD-NLT-AB05 + IL-12 DNA adjuvant followed by 1 or 2 doses of sD-NLT-AB05 + IL-12 DNA adjuvant alone or in combination with Trimer 4571 adjuvanted with 3M-052-AF + Alum to elicit humoral immune responses
2. To further evaluate and compare the ability of 2 doses of sD-NLT-AB05 + IL-12 DNA adjuvant alone or in combination with Trimer 4571 adjuvanted with 3M-052-AF + Alum to elicit cellular immune responses
3. To evaluate the durability of cellular and humoral immune responses elicited by 2 doses of sD-NLT-AB05 + IL-12 DNA adjuvant followed by 2 doses of sD-NLT-AB05 + IL-12 DNA adjuvant alone or in combination with Trimer 4571 adjuvanted with 3M-052-AF + Alum

#### Endpoints

- a) Neutralizing Ab magnitude and breadth against autologous and tier 1a HIV-1 isolates as assessed by TZM-bl neutralization assay following the third and fourth vaccinations
- b) Response rate, magnitude, and epitope specificity of HIV-1 specific IgG binding Ab responses as assessed by multiplex assay 2 weeks following third vaccination
- a) Response rate and magnitude of CD4+ and CD8+ T-cell responses measured by flow cytometry, to HIV-1-specific Env peptide pools, 2 weeks following third vaccination
- a) Magnitude and response rate of CD4+ and CD8+ T-cell responses measured by flow cytometry, to HIV-1-specific Env peptide pools 6 months post last vaccination
- b) Response rate and magnitude of HIV-1 specific IgG binding Ab responses as assessed by multiplex assay 6 months post last vaccination
- c) Neutralizing Ab magnitude and breadth against autologous tier 2 HIV-1 isolates as assessed by TZM-bl neutralization assay 6 months post last vaccination

### 3.3 Exploratory Objectives

1. To clinically evaluate EP-injection-related skin changes for 6 months after the last study product administration and subjective assessment by participant of tolerability at 12 months after the last study product administration.

2. To evaluate the response rate and magnitude of HIV-1 specific IgG binding Ab responses as assessed by multiplex assay 2 weeks following second vaccination.
3. To evaluate the response rate and magnitude of CD4+ and CD8+ T-cell responses measured by flow cytometry, to HIV-1-specific Env peptide pools, 2 weeks following the second vaccination.
4. To evaluate the frequency of Env-specific B cells measured by flow cytometry 2 weeks following the second, third, and fourth vaccinations and 6 months post last vaccination.
5. To evaluate serum Ab specificities and elicitation of trimer-degrading Abs using polyclonal epitope mapping as assessed by Electron Microscopy 2 weeks post third and fourth vaccinations.
6. To evaluate the neutralizing Ab magnitude and breadth against heterologous and tier 2 HIV-1 isolates as assessed by TZM-bl neutralization assay following the third, and fourth vaccinations.
7. To evaluate of HIV-1 specific IgG binding Ab responses to the trimer base 2 weeks following second, third, and fourth vaccinations.
8. To evaluate Ab avidity and Fc Receptor functions such as FcR binding, ADCC, antibody-dependent cellular phagocytosis (ADCP), and infected cell antibody-binding assay (ICABA) after the second, third, and fourth vaccinations.
9. To evaluate B-cell receptor (BCR) repertoires and sequences (including analysis of rare B-cell lineages associated with bnAb precursors), including cellular phenotyping and mutational frequency analysis suggestive of somatic hypermutation and affinity maturation following immunization.
10. To characterize monoclonal Abs derived from BCR sequences from Env-specific B cells.
11. To conduct analyses related to furthering the understanding of HIV, immunology, vaccines, and clinical trial conduct.
12. To further evaluate immunogenicity of each vaccine regimen, additional immunogenicity assays may be performed in a subset of participants, including on samples from other timepoints, based on the HVTN Laboratory Assay Portfolio.

#### **4 COHORT DEFINITION**

A total of 20 participants were enrolled in the study, 10 in Group 1 and 10 in Group 2.

#### **5 RANDOMIZATION**

The randomization sequence will be obtained by computer-generated random numbers and provided to each HVTN CRS through the Statistics and Data Management Center's (SDMC) Web-based randomization system. The randomization will be done in blocks to ensure balance across study groups. At each institution, the pharmacist with primary responsibility for dispensing study products is charged with maintaining security of the treatment assignments.

## 6 BLINDING

This is an open-label study. Participants and site staff will be unblinded to participants' group assignments. Laboratory program staff will be blinded to participants' group assignments during assay analysis, whenever feasible.

## 7 STATISTICAL ANALYSIS

All data from enrolled participants will be analyzed according to the initial randomization assignment regardless of how many vaccinations they received. The analysis is a modified intent-to-treat analysis in that individuals who are randomized but not enrolled do not contribute data and hence are excluded. Because of the brief length of time between randomization and enrollment—typically no more than 4 working days—very few such individuals are expected. All analyses will be performed using SAS and R. Supporting analyses will be performed restricting to subsets of participants who received the complete series of vaccinations.

No formal multiple comparison adjustments will be employed for multiple safety endpoints, multiple primary immunogenicity endpoints, or secondary endpoints. However, multiplicity adjustments will be made for certain immunogenicity assays, as discussed below, when the assay endpoint is viewed as a collection of hypotheses (eg, testing multiple peptide pools to determine a positive response).

### 7.1 Analysis Variables

The analysis variables consist of baseline participant characteristic, and immunogenicity for primary- and secondary-objective analyses.

### 7.2 General approach

For the statistical analysis of immunogenicity endpoints, data from enrolled participants will be used according to the initial randomization assignment regardless of how many injections they received. Additional analyses may be performed, limited to participants who received all scheduled injections per protocol. Assay results that are unreliable, from specimens collected outside of the visit window, or from HIV-infected participants are excluded. Since the exact date of HIV infection is unknown, any assay data from blood draws 4 weeks, or less, prior to an infected participant's last seronegative sample and thereafter may be excluded. If an HIV-infected participant does not have a seronegative sample post enrollment, then all data from that participant may be excluded from the analysis.

Discrete categorical assay endpoints (eg, response rates) will be analyzed by tabulating the frequency of positive response for each assay by antigen and treatment arm at each timepoint for which an assessment is performed. Crude response rates will be presented with their corresponding 95% CI estimates calculated using the score test method (1). Barnard's tests will be used to compare the response rates between 2 vaccine groups at a given time-point, McNemar's tests will be used for paired data (between visits), with a significant difference declared if the 2-sided p-value is  $\leq 0.05$ .

For quantitative assay data (eg, magnitude of HIV-1 Env-specific binding Ab responses), graphical and tabular summaries of the distributions by antigen, treatment arm, and timepoint will be made. The difference between arms at a specific timepoint will be tested with a nonparametric Wilcoxon rank sum test and the difference between visits will be tested with a nonparametric Wilcoxon signed rank test including all available data regardless of response positivity. Response magnitudes below the limit of detection of the assay will be replaced by half of the limit in the

tests. All statistical tests will be 2-sided and will be considered statistically significant if  $p \leq 0.05$ .

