3.2 Secondary objectives and endpoints

Objectives	Endpoints
1. To further evaluate and compare the ability of 2 doses of sD-NLT-AB05 + IL-12 DNA adjuvant followed by 1 or 2 doses of sD-NLT-AB05 + IL-12 DNA adjuvant alone or in combination with Trimer 4571 adjuvanted with 3M-052-AF + Alum to elicit humoral immune responses	a) Neutralizing Ab magnitude and breadth against autologous and tier 1a HIV-1 isolates as assessed by TZM-bl neutralization assay following the third and fourth vaccinations b) Response rate, magnitude, and epitope specificity of HIV-1 specific IgG binding Ab responses as assessed by multiplex assay 2 weeks following third vaccination
2. To further evaluate and compare the ability of 2 doses of sD-NLT-AB05 + IL-12 DNA adjuvant alone or in combination with Trimer 4571 adjuvanted with 3M-052-AF + Alum to elicit cellular immune responses	a) Response rate and magnitude of CD4+ and CD8+ T-cell responses measured by flow cytometry, to HIV-1-specific Env peptide pools, 2 weeks following third vaccination

Objectives	Endpoints

3. To evaluate the durability of cellular and humoral immune responses elicited by 2 doses of sD-NLT-AB05 + IL-12 DNA adjuvant followed by 2 doses of sD-NLT-AB05 + IL-12 DNA adjuvant alone or in combination with Trimer 4571 adjuvanted with 3M-052-AF + Alum
	
a) Magnitude and response rate of CD4 + and CD8+ T-cell responses measured by flow cytometry, to HIV-1-specific Env peptide pools 6 months post last vaccination
 
b) Response rate and magnitude of HIV-1 specific IgG binding Ab responses as assessed by multiplex assay 6 months post last vaccination
 
c) Neutralizing Ab magnitude and breadth against autologous tier 2 HIV-1 isolates as assessed by TZM-bl neutralization assay 6 months post last vaccination

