### 8.6.1 List of Tables

- Response rate table by isotype, antigen, visit, and treatment arm
- Summary statistics (i.e., min, mean, median, max) of net MFI among all participants (positive and negative responders) by isotype, antigen, visit, and treatment arm
- Summary statistics (i.e., min, mean, median, max) of net MFI among responders by isotype, antigen, visit, and treatment arm
- Summary statistics of binding antibody titers (AUC) among all participants by isotype, antigen, visit, and treatment arm

- Summary statistics of binding antibody titers (AUC) among positive responders by isotype, antigen, visit, and treatment arm
- Differential binding response rate table by differential binding antigen pairs, timepoint, and treatment group

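### Durability is tested between visits but never estimated: no interval is planned for any within-participant change, and at 9–10 per arm a non-significant McNemar test cannot support persistence

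*SAP*

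**What the plan says.** Both documents make durability a secondary objective (Protocol 3.2; SAP 3.2): "To evaluate the durability of cellular and humoral immune responses elicited by 2 doses of sD-NLT-AB05 + IL-12 DNA adjuvant", followed by two further doses with or without the adjuvanted trimer. The endpoints are levels at six months after the last dose. For binding antibody the endpoint is "Response rate and magnitude of HIV-1 specific IgG binding Ab responses as assessed by multiplex assay 6 months post last vaccination", and the T-cell and neutralization endpoints are built the same way.

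For analysis, SAP 7.2 provides:

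- Response rates by antigen, arm and timepoint: "Crude response rates will be presented with their corresponding 95% CI estimates calculated using the score test method".
- Between-visit comparison of rates: "McNemar's tests will be used for paired data (between visits), with a significant difference declared if the 2-sided p-value is" 0.05 or less.
- Between-visit comparison of magnitude: "the difference between visits will be tested with a nonparametric Wilcoxon signed rank test including all available data regardless of response positivity".

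The SAP does not say which visits are compared for durability, or whether McNemar is exact, mid-p, uncorrected or continuity-corrected.

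The table lists are by visit. BAMA (8.6.1) has a "Response rate table by isotype, antigen, visit, and treatment arm" and per-visit magnitude summaries (minimum, mean, median and maximum for net MFI). The comparison tables for ICS (8.1.1) and neutralization (8.2.1) compare arms, not visits. Spaghetti plots are planned for ICS, neutralization and BAMA, the last only if the Visit 9 response rate is at least 20%.

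**The concern.** Durability asks how much of the response seen shortly after the fourth dose (Visit 9) is still there six months after it (Visit 10). A test of no change does not answer that. A non-significant result in 9 or 10 people is compatible with losing most of the responders. A significant result says that something was lost, not how much is left.

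The natural answers are the share of Visit 9 responders still positive, the paired change in rate, and the fold change in magnitude, each with an interval. None is in the plan. Two separate per-visit intervals do not supply the paired answer, because its precision depends on how many participants switched status.

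The risk lies in the report. If the p-values are the only between-visit results, a reader may take a non-significant one as persistence. That would favour an arm with few peak responders, since such an arm has fewer losses available to reach significance.

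**Working it through.** **Inputs.** 10 enrolled per arm (SAP section 4); 9 evaluable per arm after 10% missing data (Protocol 6.1.1); two-sided 0.05 (SAP 7.2). The documents give no power or precision for a between-visit comparison and no SD of paired change, so the loss rates, peak rates and SDs below are assumptions.

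**The plan's own figure.** Protocol Table 6-1 gives 15.3–77.3% for 4 of 9. The score interval with continuity correction gives 15.3–77.3%, and all ten rows reproduce this way. The score interval without correction gives 18.9–73.3%.

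**How many losses McNemar needs.** With b responders lost and none gained:

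- Exact: p = 2 × 0.5^b. b = 5 gives 0.0625; b = 6 gives 0.031.
- Continuity-corrected: chi-square = (b − 1)²/b. b = 5 gives 3.20, p = 0.074; b = 6 gives 4.17, p = 0.041.
- Mid-p: p = 0.5^b. b = 4 gives 0.0625; b = 5 gives 0.031.
- Uncorrected: chi-square = b. b = 3 gives p = 0.083; b = 4 gives p = 0.0455.

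The minimum is therefore 6, 6, 5 and 4 losses. An arm with at most 5, 5, 4 or 3 responders at Visit 9 could lose every one without a significant result.

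One gain makes it harder. With 8 of 9 positive at Visit 9, 6 lost and 1 gained, exact p = 2 × (1 + 7)/128 = 0.125, mid-p = 0.125 − 7/128 = 0.070, uncorrected (25/7) p = 0.059, corrected (16/7) p = 0.131. All four miss the loss of 6 of 8 responders.

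**How often a true 50% loss is missed.** Losses are Binomial(n, peak rate × 0.5) with no gains. The probability of non-significance is the probability of fewer losses than the minimum.

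| Pairs | Version | Peak 90% | Peak 70% | Peak 60% |
|---|---|---|---|---|
| 9 | exact or corrected | 83% | 95% | 98% |
| 9 | mid-p | 62% | 83% | 90% |
| 9 | uncorrected | 36% | 61% | 73% |
| 10 | exact or corrected | 74% | 91% | 95% |
| 10 | mid-p | 50% | 75% | 85% |
| 10 | uncorrected | 27% | 51% | 65% |

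**Magnitude.** Simulated exact signed rank test, 9 pairs, normal paired log10 differences, SD 0.3 to 0.5 (assumed), 40,000 runs per setting:

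| True decline | Significant (SD 0.5 to SD 0.3) |
|---|---|
| 1.25-fold | 6% to 11% |
| 1.5-fold | 12% to 29% |
| 2-fold | 31% to 68% |
| 3-fold | 64% to 97% |
| 10-fold | over 99% |

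At SD 0.3 to 0.4, both a 3-fold and a 10-fold fall are usually significant (83% or more), so the p-value hardly separates them. A geometric mean ratio would: its 95% limits lie a factor of 10^(2.306 × SD/√9) either side, which is 1.7 at SD 0.3, 2.0 at 0.4 and 2.4 at 0.5.

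**What an estimate would show.** Suppose 5 of 9 peak responders are lost and none gained. Retention is 4/9 = 44% (score interval 19–73%). For the paired fall, the Bonett–Price adjusted Wald interval uses (5 + 1)/11 − (0 + 1)/11 = 0.455, with SE = √[(7/11 − 0.455²)/11] = 0.198, giving 0.455 ± 1.96 × 0.198, or 7 to 84 points. Exact McNemar reports only p = 0.0625.

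**The case against.** The strongest reply is that the endpoints as written are levels at Visit 10, and that the response rate there does have a score interval. This stands. A reader might infer that nothing about durability has an interval; SAP 7.2 shows otherwise for marginal rates. What lacks an interval is any paired quantity, and magnitude altogether.

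Second, a reader might infer that the plan treats non-significance as durability. It does not. McNemar is listed as a general between-visit test, no persistence margin is set, and spaghetti plots will show each trajectory. The concern is that the planned tests cannot support a persistence statement and nothing planned replaces them.

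Third, a reader might expect signed rank to declare a decline however well the response is kept. The simulation contradicts this: a 1.25-fold fall is significant in only 6–11% of runs and a 1.5-fold fall in 12–29%.

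Fourth, the McNemar figures depend on a version the SAP does not state, and the exact test is the least favourable. Under mid-p or the uncorrected test, 5 of 9 lost would be significant. Even so, at a 90% peak rate the best case in the table still misses a 50% loss 27% of the time.

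Finally, Protocol 6.4.4.2 allows optional repeated-measures models, while warning that the small sample limits inference, and 6.4.4.3 specifies mixed models if more than 20% of participants have missing values. Either could have yielded paired estimates. SAP 7.2 and 7.3 carry over neither.

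**Conclusion.** The point holds as a gap in estimation for a secondary objective. SAP 7.2 gives marginal rates with intervals, magnitude summaries without them, plots, and two between-visit tests with an unnamed visit pair and an unnamed McNemar version. It plans no interval for retention, paired rate change or fold change.

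With a true 50% loss among responders, McNemar on 9 pairs misses it in 36–98% of cases, depending on version and a peak rate of 60–90%; on 10 pairs, in 27–95%. These figures assume independent losses and no gains. The magnitude results rest on an assumed paired log10 SD of 0.3–0.5. Reading durability as change from Visit 9 to Visit 10 is an interpretation: it fits the objective, but neither document names that pair.

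**What to change.** In SAP 7.2 and the table lists of 8.1, 8.2 and 8.6, name Visit 10 versus Visit 9 as the durability contrast and report, by arm:

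1. The proportion of Visit 9 responders still positive at Visit 10, and the paired change in response rate, each with a 95% interval by a named method.
2. The Visit 10/Visit 9 geometric mean ratio with 95% interval for neutralizing titre and for BAMA (AUC if samples are titrated, otherwise net MFI), and the paired median change with 95% interval for background-adjusted ICS.

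Show each magnitude measure for all participants with both visits and for Visit 9 responders. Note that the all-participant ratio is affected by replacing values below the detection limit with half that limit.

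Keep McNemar, with its version stated, and signed rank as supportive. State that a non-significant between-visit test will not be reported as evidence of durability. Because the interval and the test can disagree at this size (7 to 84 points against exact p = 0.0625), say that the interval is the main result.

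The cost is SAP wording and one added table per assay, with no new samples or participants. The intervals will be wide and will show how little 9 or 10 per arm can say about persistence of response rates. If Visit 10 results have already been reported by arm, label the tables as added afterwards.
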